1.3 Clinical Experience

Ixazomib is the first investigational oral proteasome inhibitor to enter clinical trials. Phase 1, phase 1/2, and phase 2 trials are ongoing in MM, systemic light-chain amyloidosis (AL amyloidosis), solid tumors, and lymphoma. In addition, phase 1 studies are ongoing in patients with renal impairment who have relapsed and/or refractory multiple myeloma (RRMM) or advanced solid tumors (Study C16015), in patients with hepatic impairment who have advanced solid tumors or hematologic malignancies (Study C16018), and in an absorption, distribution, metabolism, and excretion (ADME) study in patients with advanced solid tumors or lymphoma (Study C16016). Phase 3 trials in RRMM, newly diagnosed multiple myeloma (NDMM), and relapsed or refractory systemic light-chain amyloidosis (RRAL amyloidosis) are underway.

As of 27 March 2015, data are available from 901 patients who have received at least 1 dose of either the IV or oral ixazomib formulations across the clinical development program; in addition, 1513 patients have enrolled in 4 phase 3 clinical trials: 1) Placebo-controlled Study C16010 and Study C16010 China continuation study (CCS) of ixazomib versus placebo in combination with LenDex in patients with RRMM; 2) Placebo-controlled Study C16014 of ixazomib versus placebo in combination with LenDex in patients with NDMM; 3) Placebo-controlled Study

C16019 of ixazomib versus placebo in patients with NDMM; 4) Open-label Study C16011 of ixazomib and dexamethasone versus physician's choice of a dexamethasone-containing regimen in patients with AL amyloidosis. Ixazomib is available as an IV and oral formulation; however, only the oral formulation is currently being developed for commercialization. Regardless of the route of administration, in the twice-weekly dosing schedule ixazomib is given on Days 1, 4, 8, and 11 of a 21-day cycle, and in the weekly dosing schedule ixazomib is given on Days 1, 8, and 15 of a 28-day cycle. Schedules with longer cycles are being investigated in Study C16006.

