1.5 Clinical Trial Experience Using the Oral Formulation of Ixazomib

As of 27 March 2015, a total of 755 patients with differing malignancies (MM, AL amyloidosis, lymphoma, and nonhematologic cancers) have received at least 1 dose of ixazomib in phase 1, phase 1/2, and phase 2 studies evaluating the oral ixazomib formulation. These patients have been treated with different doses of ixazomib either as a single-agent treatment (163 patients), in combination with currently clinically available treatments (370 patients), or in clinical pharmacology/special population studies (208 patients). In addition, 1513 patients have enrolled in phase 3 Studies C16010, C16010CCS, C16014, C16019 (double-blind, placebo-controlled studies in MM), and Study C16011 (open-label study in AL amyloidosis).

Table 1-1 Clinical Studies of Oral Ixazomib

Trial/ Population	Description	Doses Investigated
C16003 RRMM N = 60	PO, TW, single agent	0.24-2.23 mg/m ² TW MTD: 2.0 mg/m ² DLT: rash, thrombocytopenia Closed to enrollment
C16004 RRMM N = 60	PO, W, single agent	0.24-3.95 mg/m ² W MTD: 2.97 mg/m ² DLT: rash, nausea, vomiting, diarrhea Closed to enrollment
C16005 NDMM N = 65	PO, W, combination with LenDex 28-day cycle	1.68-3.95 mg/m ² W MTD: 2.97 mg/m ² DLT: nausea, vomiting, diarrhea, syncope RP2D ^a : 4.0 mg fixed (switched to fixed dosing in phase 2, equivalent to 2.23mg/m ²) Closed to enrollment
C16006 NDMM N = 20	PO, TW (Arm A- 42 day cycle) and W (Arm B- 28 day cycle), combination with Melphalan and Prednisone	Arm A ^a : 3-3.7-mg fixed dose TW DLT: rash, thrombocytopenia, subileus Arm B ^a : 3-5.5-mg fixed dose, W DLT: Esophageal ulcer nausea, vomiting, hematemesis, thrombocytopenia, ileus, neurogenic bladder MTD = 3.0 mg
C16007 RRAL N = 27	PO, W, single agent	4-5.5-mg fixed dose ^a W DLT: thrombocytopenia, diarrhea, dyspnea, acute rise in creatinine, cardiac arrest MTD: 4.0 mg W
C16008 NDMM N = 64	PO, TW, combination with LenDex 21-day cycle	3.0-3.7-mg fixed dose ^a W MTD: 3.0 mg Closed to enrollment
C16009 Solid tumors, Lymphomas N = 54	PO, W, single agent	5.5-mg fixed dose ^a W
C16010 RRMM N = 200	PO, W, with LenDex versus placebo- LenDex	4.0 mg W
C16011 RRAL N = 4	PO, W, with Dex versus physician's choice of a Dex-based regimen	4.0 mg W
C16013 RRMM N = 9	PO, W, with LenDex	4.0 mg W

Table 1-1 Clinical Studies of Oral Ixazomib

Trial/ Population	Description	Doses Investigated

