C16014 Symptomatic MM N=701	PO, combination with LenDex	ixazomib 4.0 mg or matching placebo on Days 1, 8, and 15, plus Len 25 mg on Days 1-21 (10 mg if low creatinine clearance, with escalation to 15 mg if tolerated) and Dex 40 mg (or 20 mg if >75 years old) on Days 1, 8, 15, and 22
C16015 Symptomatic MM with normal renal function or severe renal impairment N=28	PO, combination with Dex	Part A: ixazomib 3.0 mg on Day 1 Part B: ixazomib 4.0 mg on Days 1, 8, and 15, plus Dex 40 mg (or 20 mg if >75 years old) on Days 1, 8, 15 and 22 of a 28-day cycle
C16017 RR follicular lymphoma N=58	PO, W	4.0, 5.3, and 7.0 mg, W Treatment at RP2D once determined.
C16018 Advanced solid tumors or hematologic malignancies with varying degrees of liver dysfunction N=45	Part A: PO, Day 1 of 15-day cycle Part B: PO, W	1.5 mg (severe hepatic impairment), 2.3 mg (moderate hepatic impairment), or 4.0 mg (normal hepatic function)
TB- MC010034 RRMM N = 10	PO, W	4.0 mg, W Single agent: 4.0 mg Combination with Rd

Abbreviations: RRAL = Relapsed and/or refractory Primary systemic light chain (AL) amyloidosis; BSA = body surface area; Dex=dexamethasone; DLT = dose-limiting toxicity; IV = intravenously; LenDex = lenalidomide plus dexamethasone; MTD = maximum tolerated dose; NDMM = newly diagnosed multiple myeloma; PO = orally; RR= relapsed and/or refractory; RRAL= relapsed and/or refractory systemic light chain amyloidosis RRMM = relapsed and/or refractory multiple myeloma; TBD = to be determined; TW = twice weekly; W = weekly; RP2D= recommended phase 2 dose.

Note that blinded data from pivotal Studies C16010 and C16011 are not included.

a Approximate BSA and fixed dosing equivalence: 3 mg~ equivalent to 1.68 mg/m² BSA dosing; 4.0 mg ~ equivalent to 2.23 mg/m² BSA dosing; and 5.5 mg~ equivalent to 2.97 mg/m² BSA dosing.

Overview of the Oral Formulation of Ixazomib

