1.6 Relapsed and/or Refractory Multiple Myeloma

The early development of ixazomib in patients with RRMM involves 2 studies (C16003 and C16004) with similar objectives, but each investigated 1 of the 2 dosing schedules commonly used with the first-in-class proteasome inhibitor, bortezomib.

Study C16003 is an open-label, dose escalation, phase 1 study of ixazomib dosing on

a twice-weekly schedule on Days 1, 4, 8, and 11 of a 21-day cycle in adult patients with RRMM [10]. Study C16004 is an open-label, dose escalation, phase 1 study of ixazomib dosing on a weekly schedule on Days 1, 8, and 15 of a 28-day cycle in adults patients with RRMM. Both studies have now completed enrollment. The DLTs in Study C16003 were rash macular and thrombocytopenia and the DLTs in C16004 were nausea, diarrhea, vomiting, and erythema multiforme.

In the dose escalation component of both studies, patients had multiple myeloma that had relapsed following at least 2 lines of therapy that must have included bortezomib, thalidomide (or lenalidomide), and corticosteroids. In both studies, when the MTD was established, cohorts of patients representing the heterogeneous patient population currently seen in clinical practice were to be enrolled into 1 of 4 expansion cohorts, including a relapsed and refractory cohort, a carfilzomib cohort, a proteasome inhibitor-naïve cohort, and a bortezomib-relapsed cohort.

Final study results are currently being analyzed, but preliminary data suggest that ixazomib has anti-tumor activity in heavily pretreated MM patients, with durable responses/disease control, and is generally well tolerated. Please refer to the ixazomib IB and SMA for further information.

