Ixazomib is a novel second-generation, orally bioavailable proteasome inhibitor (PI) that has shown promising preclinical efficacy in B-NHL models and success in an early-phase clinical trial in heavily pretreated, relapsed/refractory B-NHL [5]; it is approved by the FDA for use in relapsed MM. The ubiquitin-proteasome system (UPS) participates in the regulation of cellular proliferation, apoptosis, and cycle progression. Proteasome inhibition represents a well-described mechanism for disrupting cellular protein homeostasis, and, consequently, the health of a cell. The pathogenesis of B-NHL involves pathways whose components are processed by the UPS, including cyclins, members of the Bcl-2 protein family, and transcription factors NF- κ B and c-Myc [11]. Inhibition of proteasome activity with the first-generation PI bortezomib showed benefit as mono-therapy in several types of lymphomas, including MCL [12] and various B-NHL histologies in the relapsed or refractory setting [13, 14]. Ixazomib possesses improved tissue penetration and antitumor activity *in vitro* compared with bortezomib [15] and thus represents a promising, novel approach in treating B-NHL. Importantly, emerging safety profile indicates that oral ixazomib is generally well tolerated with predominant toxicities that are largely reversible, able to be monitored by routine clinical examinations and manageable by dose reductions, discontinuation, or standard supportive care, making it an ideal candidate for upfront window testing in B-NHL previously untreated with standard systemic therapy.

The rationale for this study is to evaluate the efficacy of ixazomib in untreated, indolent B-NHL and gain a preliminary assessment of the ceiling of activity of this agent as monotherapy in these diseases.

To minimize the risk to patients receiving potentially ineffective first-line therapy with an experimental agent, a standard course of rituximab at a dose of 375 mg/m² per week x4 will be added after completion of 6 cycles of ixazomib monotherapy.

Rituximab as a single agent has broad activity in B-cell malignancies and established efficacy as a single agent in the indolent B-NHL to be studied herein.

The fixed dose of 4 mg PO weekly was selected based on several dose-escalation phase I ixazomib monotherapy studies (e.g. C16004 and C16009) that identified the MTD at this dose or higher.

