6.2 Study Drug Administration

Ixazomib Administration

All protocol-specific criteria for administration of study drug must be met and documented before drug administration. Study drug will be administered or dispensed only to eligible patients under the supervision of the investigator or identified sub-investigator(s). Patients should be monitored for toxicity, as necessary, and doses of ixazomib should be modified as needed to accommodate patient tolerance to treatment; this may include symptomatic treatment, dose interruptions, and adjustments of ixazomib dose (see Section 6.2).

Capsules of ixazomib will also be referred to as study drug. Study drug will be supplied by Millennium as capsules of 0.2, 0.5, and 2.0 mg, or as capsules of 2.3, 3.0 and 4.0 mg ixazomib, depending on available ixazomib formulation.

The prescribed administration of ixazomib doses in this study is 4 mg ixazomib q7 days in a q28 day cycle. Sufficient drug will be dispensed for each interval of evaluation at the FHCC, that is, either for 1 or 2 cycles of therapy.

Patients should be instructed to swallow ixazomib capsules whole, with water, and not to break, chew, or open the capsules. Study drug should be taken on an empty stomach (no food or drink) at least 1 hour before or 2 hours after a meal. Each capsule should be swallowed separately with a sip of water. A total of approximately 8 ounces (240 mL) of water should be taken with the capsules.

Missed doses can be taken as soon as the patient remembers if the next scheduled dose is 72 hours or more away. A double dose should not be taken to make up for a missed dose. If the patient vomits after taking a dose, the patient should not repeat the dose but should resume dosing at the time of the next scheduled dose.

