6.3 Administration of Rituximab

Rituximab will be administered at a standard dose of 375 mg/m² by intravenous infusion weekly for 4 consecutive weeks upon completion of the 6-cycle window period of ixazomib monotherapy. Rituximab will be administered per institution standard treatment plan with medications for infusion-reaction prophylaxis and/or treatment given at the discretion of the investigator. Ixazomib will be continued uninterrupted during and after the rituximab therapy. Dose modification or delay to rituximab may be made according to the discretion of the investigator.

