6.4 Dose-Modification Guidelines

Study drug dose modifications may change depending on the disease and combination with other drug(s).

If a new combination study, an attempt should be made to integrate dose modifications for the combination for each AE.

6.4.1 Recommended Ixazomib Criteria for Beginning or Delaying a Subsequent Treatment Cycle & Dose Modifications for Treatment Associated Toxicity

Treatment with ixazomib will use a cycle length of 28 days. For a new cycle of treatment to begin, the patient must meet the following criteria:

- ANC must be $\geq 500/\text{mm}^3$.
- Platelet count must be $\geq 50,000/\text{mm}^3$.
- Non-hematologic toxicities, attributable to ixazomib (except for alopecia) and which required a dose hold, should, at the physician's discretion, generally be recovered to \leq Grade 1 or the patient's baseline condition.

If the patient fails to meet the above-cited criteria for initiation of the next cycle of treatment, dosing should be delayed for 1 week. At the end of that time, the patient should be re-evaluated to determine whether the criteria have been met. If the patient continues to fail to meet the above-cited criteria, delay therapy and continue to reevaluate. The maximum delay before treatment should be discontinued will be 3 weeks or at the discretion of the Principal Investigator and/or Sub-Investigator.

For dosing recommendations upon recovery, refer to Table 6-2 and Table 6-3.

Table 6-1 Ixazomib Dose Adjustments

Dose Level	Dose (mg)
Starting Dose	4.0 mg
-1	3.0 mg
-2	2.3 mg
-3	Discontinue

Dosage adjustments for hematologic toxicity are outlined in Table 6-2.

Table 6-2 Ixazomib Dose Adjustments for Hematologic Toxicities

Criteria	Action
Platelet count less than 30,000/mm ³	
 • Hold Ixazomib dose. • Once the platelet counts have met the prespecified values (see Section 6.4.1), ixazomib may be reinitiated at its most recent dose. • If platelet count falls to less than 30,000/mm³, hold ixazomib until counts have met the prespecified values (see Section 6.4.1) and then resume ixazomib at the next lower dose.

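### The Table 6-2 hold limits have no required on-treatment blood count behind them at the Day 15 and Day 22 doses of Cycle 1; the mid-cycle count, now only recommended, should be mandatory

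*Combined protocol and SAP*

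**What the plan says.** **Dosing.** Section 6.2 states: "The prescribed administration of ixazomib doses in this study is 4 mg ixazomib q7 days in a q28 day cycle". That is four doses per cycle (Days 1, 8, 15 and 22). Drug is dispensed for one or two cycles at a time (6.2, 6.11). Section 6.3 adds: "Ixazomib will be continued uninterrupted during and after the rituximab therapy".

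**Cycle-start criteria.** Section 6.4.1 introduces them with "For a new cycle of treatment to begin, the patient must meet the following criteria"; they include ANC of at least 500/mm3 and platelets of at least 50,000/mm3.

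**Hold limits.** Table 6-2 holds ixazomib at platelets below 30,000/mm3 or ANC below 500/mm3. Dosing resumes once the 6.4.1 values are met, and at the next lower dose after a repeat fall.

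**Entry.** Section 5.1 requires ANC of at least 1,000/mm3, or 500/mm3 if neutropenia is attributed to B-NHL. Platelets must be at least 100,000/mm3, or 75,000/mm3 if the low count is attributed to B-NHL.

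**Counts.** Footnote 10 of the Schedule of Events requires labs on Day 1 of each cycle (plus or minus 3 days through Cycle 8). For Cycle 1 Day 1, labs up to 14 days old are accepted. The one mid-cycle draw it names, Cycle 1 Day 14 plus or minus 3 days, is strongly advised but not required. Section 6.8 refers back to the schedule and leaves further testing to standard practice.

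**The concern.** A hold rule protects a patient only if someone has the number to which it applies. Table 6-2 sets limits for withholding a dose, and its platelet limit makes full sense only between cycle starts, when no count is required.

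The first cycle matters most, because nothing is yet known about how the patient's counts respond to the drug. The capsules are at home, and the Cycle 1 Day 14 clinic assessment is also only recommended (footnote 9). A fall in neutrophils or platelets without symptoms could therefore pass unnoticed while two more doses are taken. What is at stake is individual patient safety and whether the protocol's own dose rules can be applied as written. The response-rate test is not affected.

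**Working it through.** The plan states no figure to reproduce here. The check sets its rules side by side and counts days.

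**1. What each limit does at cycle start and within a cycle**
- Platelets: below 50,000/mm3 on Day 1 already stops the cycle from starting. A hold at below 30,000/mm3 adds nothing to that decision, though it may affect the dose on resumption. As an instruction to hold, it acts alone only before the Day 8, 15 and 22 doses.
- ANC: the cycle-start and hold limits are the same value, 500/mm3.

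**2. Distance from the lowest permitted entry value to the hold limit**
- ANC: 500 − 500 = 0/mm3 if neutropenia is attributed to B-NHL; otherwise 1,000 − 500 = 500/mm3.
- Platelets: 75,000 − 30,000 = 45,000/mm3 if attributed to B-NHL; otherwise 100,000 − 30,000 = 70,000/mm3.

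**3. Time on drug without a required count in Cycle 1**
- Day 15 dose: 15 − 1 = 14 days after the first dose.
- Day 22 dose: 22 − 1 = 21 days after the first dose.
- Next required count: Cycle 2 Day 1 = Day 29, window Day 26 to Day 32, which is 25 to 31 days after the first dose. Even the earliest date is after the Day 22 dose.

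**4. The recommended draw**
- Its window is Day 14 ± 3 = Day 11 to Day 17. Days 16 and 17 come after the Day 15 dose, so even a compliant draw may miss it.
- With a required window of Day 11 to Day 15, the count is 15 − 15 = 0 to 15 − 11 = 4 days old at the Day 15 dose, and 22 − 15 = 7 to 22 − 11 = 11 days old at the Day 22 dose.

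**5. Are cytopenias relevant with this drug?** Table 1-2 (oral single-agent studies, 201 patients) lists thrombocytopenia in 68 (34%) and neutropenia in 29 (14%). The table gives neither grade nor timing and pools different schedules, so it cannot say how many of the 36 patients would cross a limit.

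**6. Side calculation: 28-day total against the cited MTD.** Section 1.9 rests the dose on "several dose-escalation phase I ixazomib monotherapy studies (e.g. C16004 and C16009) that identified the MTD at this dose or higher". Section 1.6 says "Study C16004 is an open-label, dose escalation, phase 1 study of ixazomib dosing on a weekly schedule on Days 1, 8, and 15", three doses per 28 days. Table 1-1 gives that study's MTD as 2.97 mg/m2, and its footnote gives approximate conversions, including "and 5.5 mg~ equivalent to 2.97" mg/m2.
- Total here: 4 × 4 = 16 mg.
- At 5.5 mg per dose: 16 / (3 × 5.5) = 16 / 16.5 = 0.970.
- In mg/m2, with 4.0 mg taken as 2.23: (4 × 2.23) / (3 × 2.97) = 8.92 / 8.91 = 1.001.
- With 3 mg taken as 1.68 mg/m2: 2.97 × 3 / 1.68 = 5.304 mg; 16 / (3 × 5.304) = 16 / 15.91 = 1.006.
- Per dose: 4 / 5.5 = 0.727; 2.23 / 2.97 = 0.751; 4 / 5.304 = 0.754.
- If body surface area is varied as an assumption, 16 / (3 × 2.97 × BSA) is 1.20 at 1.5 m2, 1.00 at 1.8 m2 and 0.90 at 2.0 m2.

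**The case against.** **Existing controls.** Section 6.2 requires administration criteria to be met and documented before dosing and asks for toxicity monitoring as necessary. The Cycle 1 Day 14 draw is strongly advised, and 6.8 allows more testing. A careful site will probably draw the count. This stands in part: it makes the gap smaller in practice, but none of these texts requires a count before the Day 15 or Day 22 dose, and drug for one or two cycles has already been dispensed.

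**Platelet buffer.** Entry values leave 45,000 to 70,000/mm3 before the hold limit, and patients without prior standard systemic therapy may tolerate the drug better than the pretreated patients in C16004. Both points stand; the zero distance applies only to ANC in disease-related neutropenia.

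**Length of the gap.** One could say that the last required count may be 35 days old at the Day 22 dose. That includes up to 14 days before any drug was given. The on-drug figure is 21 days.

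**Reading the dose total as a warning.** Because the 16 mg total is close to the C16004 MTD total, a reader might infer that the schedule is too toxic, or that cytopenia is to be expected. The documents do not support this. Section 1.6 gives the C16004 dose-limiting toxicities as gastrointestinal events and erythema multiforme, which a blood count would not detect. Each dose is 73–75% of that MTD, and nothing in the protocol says that tolerability follows the 28-day total. Table 1-1 does list thrombocytopenia among the dose-limiting toxicities of C16007, a weekly single-agent study ("DLT: thrombocytopenia, diarrhea, dyspnea, acute rise in creatinine, cardiac arrest MTD: 4.0 mg W"), but that was in amyloidosis and 1.9 does not name it.

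**Unrecorded holds.** A reader might also infer that holds for low counts go unreported. Under 8.1.1, a laboratory value that delays treatment is an adverse event and so is captured.

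**Conclusion.** The point holds as a gap between a dose rule and the data needed to apply it. In Cycle 1, the Day 15 and Day 22 doses can be taken after 14 and 21 days on drug with no required on-treatment count. A mandatory count would reduce the age of the latest result to 0–4 and 7–11 days. This is a cheap improvement to patient safety and no evidence of harm: the documents do not show how often a limit would be crossed, and many sites may already follow the recommendation.

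The conclusion assumes that footnote 10 is the full list of required counts and that weekly doses fall on Days 1, 8, 15 and 22. The Day 8 dose and later cycles also lack a required within-cycle count, but from Cycle 2 at least one on-treatment result is known.

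The 28-day total, 97–101% of the C16004 MTD total by the protocol's approximate conversions and 90–120% across BSA of 2.0 to 1.5 m2, is a side note. Section 1.9 compares single doses and does not mention that the cited schedule had a rest week. That is not a ground for the fix.

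**What to change.** In footnote 10, make a CBC with differential required once between Day 11 and Day 15 of Cycle 1, with the result reviewed before the Day 15 dose, and state that Table 6-2 applies to it.

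If a limit is crossed, hold and resume under 6.4.1 and Table 6-2. Do not use the 72-hour missed-dose rule in 6.2 for this purpose: it would allow a dose on Day 19 (22 − 3) followed by the Day 22 dose, two doses only 3 days apart.

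**Cost.** One footnote is edited, and one draw that is now recommended becomes mandatory. Footnote 10 already allows a local laboratory. A missed draw becomes a protocol deviation. Dose, sample size and endpoints do not change.

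**Reach.** Only patients who have yet to start Cycle 1 benefit. The document is dated 27 December 2023, accrual was planned for 1–2 years, and 4.4 sets a stop to study treatment at 5 years or one year after 15 November 2022, whichever is later. Accrual status is not stated, so the change may reach few patients or none.
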